10.3 Expectedness

- Expected: Expected adverse events are those that have been previously identified as resulting from administration of the agent. For the purposes of this study, an adverse event is considered expected when it appears in the current adverse event list, the Investigator's Brochure (8.0), the package insert or is included in the informed consent document as a potential risk.
- Unexpected: An adverse event is considered unexpected when it varies in nature, intensity or frequency from information provided in the current adverse event list, the Investigator's Brochure (8.0), the package insert or when it is not included in the informed consent document as a potential risk

10.4 Attribution

Attribution is the relationship between an adverse event or serious adverse event and the study treatment. Attribution will be assigned as follows:

- Definite – The AE is clearly related to the study treatment.
- Probable – The AE is likely related to the study treatment.
- Possible – The AE may be related to the study treatment.
- Unlikely - The AE is doubtfully related to the study treatment.
- Unrelated - The AE is clearly NOT related to the study treatment.

10.5 REPORTING PROCEDURES

All adverse events will be captured on the appropriate study-specific case report forms (CRFs).

10.6 INSTITUTIONAL REVIEW BOARD

Institutional Review Board

All adverse events and serious adverse events will be reported to the IRB per current institutional standards. If an adverse event requires modification of the informed consent, these modifications will be provided to the IRB with the report of the adverse event. If an adverse event requires modification to the study protocol, these modifications will be provided to the IRB as soon as is possible

11. DATA AND SAFETY MONITORING PLAN

This is a DSMP Level I study under the SKCCC Monitoring Plan. A Level I study requires both internal and external data monitoring. The Principal Investigator is responsible for internal monitoring for both safety and data quality. External data monitoring will be performed by the SKCCC at Johns Hopkins Clinical Research Office Quality Assurance Program (CRO QA).

Data and safety monitoring oversight will be conducted by the SKCCC at Johns Hopkins Safety Monitoring Committee. Per the SKCCC at Johns Hopkins Safety Monitoring plan, the CRO AQ will forward summaries of all monitoring reports to the Safety Monitoring Committee for review. All reportable anticipated and unanticipated protocol events/problems and amendments that are submitted to the IRB will also be reviewed by the Safety Monitoring Committee Chair (or designee) and QA manager.

12. REGULATORY CONSIDERATIONS

Information regarding study conduct and progress will be reported to the Institutional Review Board (IRB) per the current institutional standards.

12.2 Informed Consent

The investigator (or his/her designee) will explain to each subject the nature of the study, its purpose, the procedures involved, the expected duration, the potential risks and benefits involved and any discomfort it may entail. Each subject will be informed that participation in the study is voluntary, that she may withdraw from the study at any time, and that withdrawal of consent will not affect her subsequent medical treatment or relationship with the treating physician(s) or institution. The informed consent will be given by means of a standard written statement, written in non-technical language, which will be IRB approved. The subject should read and consider the statement before signing and dating it, and will be given a copy of the document. No subject will enter the study or have study-specific procedures done before his/her informed consent has been obtained.

In accordance with the Health Information Portability and Accountability Act (HIPAA), the written informed consent document (or a separate document to be given in conjunction with the consent document) will include a subject authorization to release medical information to the study sponsor and supporting agencies and/or allow these bodies, a

October 10, 2023

Principal Investigator: [name]

IRB IRB00128074

regulatory authority, or Institutional Review Board access to subjects' medical information that includes all hospital records relevant to the study, including subjects' medical history.

12.3 Ethics and GCP

This study will be carried out in compliance with the protocol and Good Clinical Practice, as described in:

1. ICH Harmonized Tripartite Guidelines for Good Clinical Practice 1996.
2. US 21 Code of Federal Regulations dealing with clinical studies (including parts 50 and 56 concerning informed consent and IRB regulations).
3. Declaration of Helsinki, concerning medical research in humans (Recommendations Guiding Physicians in Biomedical Research Involving Human Subjects, Helsinki 1964, amended Tokyo 1975, Venice 1983, Hong Kong 1989, Somerset West 1996).

The investigator agrees to adhere to the instructions and procedures described in it and thereby to adhere to the principles of Good Clinical Practice that it conforms to.

12.4 PROTOCOL REVIEW AND AMENDMENTS

Any changes to the protocol will be made in the form of an amendment and must be approved by the IRB prior to implementation.

13. STATISTICAL CONSIDERATIONS

This is a prospective, single-arm study to determine the pathologic outcomes, acute toxicities, cosmetic outcomes, and local recurrence rates of preoperative single fraction partial breast radiation in early stage breast cancer. All analyses will be undertaken in the enrolled population who initiate treatment.

13.1 Primary analysis, sample size, accrual and monitoring

The pCR and RCB status as assessed at surgery (defined in Section 2) will be tabulated, and the number and percentage of patients who achieve RCB 0/pCR or RCB 1 will be reported with two-sided 90% CIs. The primary endpoint will be rate of RCB 0 or 1.

Simon's two-stage design (Simon, 1989) will be used. The null hypothesis that the true response rate is 0.1 will be tested against a one-sided alternative. In the first stage, 16 patients will be accrued. If there are 1 or fewer responses in these 16 patients, a study team will be convened to determine if the study should proceed. Otherwise, 24 additional patients will be accrued for a total of 40. The null hypothesis will be rejected if 7 or more responses are observed in 40 patients. This design yields a type I error rate of 0.089 and power of 86.9% when the true response rate is 0.25.

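### Does a two-sided 90% interval beside a one-sided test at 0.089 give the primary endpoint two conflicting answers?

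*Combined protocol and SAP*

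**What the plan says.** Section 13.1 gives the primary endpoint, the rate of RCB 0 or 1, two outputs in two paragraphs.

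- **Reporting.** RCB status is tabulated, and "the number and percentage of patients who achieve RCB 0/pCR or RCB 1 will be reported with two-sided 90% CIs". No interval method is named.
- **Decision.** The design is a Simon two-stage one. On the hypothesis, the section says: "The null hypothesis that the true response rate is 0.1 will be tested against a one-sided alternative". Stage 1 takes 16 patients, with this provision for a low count: "If there are 1 or fewer responses in these 16 patients, a study team will be convened to determine if the study should proceed". With 2 or more responses, stage 2 adds 24 patients and brings the number to 40. The final criterion is: "The null hypothesis will be rejected if 7 or more responses are observed in 40 patients". The claimed properties are: "This design yields a type I error rate of 0.089 and power of 86.9% when the true response rate is 0.25".

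No sentence links the two paragraphs. The plan does not require the interval to exclude 10%, and it does not label the interval as descriptive.

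**The concern.** A reader expects a test and a confidence interval for the same quantity to agree. Here the test spends 8.9% in one tail and the interval leaves 5% there, so the interval corresponds to a stricter test. The mismatch shows at the rejection boundary. A trial that ends with 7 of 40 would declare the rate above 10% and print beside that an interval with 10% inside it.

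If the interval were used to judge the result, the working cut-off would be 8, not 7. The power on which 40 patients were justified would then no longer apply. A related worry is that an ordinary binomial interval takes no account of the two-stage sampling.

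**Working it through.** **Inputs (all from section 13.1).** n1 = 16; review at 1 or fewer responses; n = 40 (16 + 24); reject at 7 or more; p0 = 0.10; p1 = 0.25; two-sided 90% interval, so 5% per tail.

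**Step 1. Reproduce the plan's figures.** Treat 1 or fewer responses in stage 1 as a stop. Then

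P(reject | p) = Σ over x = 2 to 16 of P(X1 = x | 16, p) × P(X2 ≥ 7 − x | 24, p).

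At p = 0.10 the terms for x = 2, 3, 4, 5, 6 and 7 are:

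| x | P(X1 = x) | P(X2 ≥ 7 − x) | Product |
|---|---|---|---|
| 2 | 0.27452 | 0.08507 | 0.02335 |
| 3 | 0.14234 | 0.21426 | 0.03050 |
| 4 | 0.05140 | 0.43573 | 0.02240 |
| 5 | 0.01371 | 0.70752 | 0.00970 |
| 6 | 0.00279 | 0.92023 | 0.00257 |
| 7 | 0.00044 | 1 | 0.00044 |

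Larger x adds less than 0.0001. The total is 0.0890. The same sum at p = 0.25 is 0.8690. Both match the plan.

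If the stage 1 look never stops the trial, the rule is a plain binomial one: P(X ≥ 7 | 40, 0.10) = 0.0995 and P(X ≥ 7 | 40, 0.25) = 0.9038.

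**Step 2. The interval at the boundary.** The exact (Clopper-Pearson) 90% limits at 7/40 solve P(X ≥ 7 | 40, p) = 0.05 and P(X ≤ 7 | 40, p) = 0.05, which gives 0.0851 and 0.3037. Lower limits by method:

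| Method | 90%, 7/40 | 90%, 8/40 | 80%, 7/40 |
|---|---|---|---|
| Clopper-Pearson | 0.0851 | 0.1036 | 0.1001 |
| Two-stage tail inverted | 0.0874 | 0.1050 | 0.1029 |
| Mid-P | 0.0925 | 0.1114 | 0.1085 |
| Jeffreys | 0.0943 | 0.1131 | 0.1100 |
| Agresti-Coull | 0.0958 | 0.1149 | 0.1103 |
| Wilson | 0.0978 | 0.1165 | 0.1113 |
| Wald | 0.0762 | 0.0960 | 0.0980 |

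All seven 90% intervals contain 0.10 at 7/40. All but Wald exclude it at 8/40. At 6/40 the rule does not reject, and the exact 90% lower limit is 0.0674, so rule and interval agree again.

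**Step 3. How often the trial ends at exactly 7.** This is P(≥ 7) − P(≥ 8) under the two-stage rule.

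- p = 0.10: 0.0890 − 0.0391 = 0.0499
- p = 0.15: 0.129
- p = 0.175: 0.142
- p = 0.20: 0.131
- p = 0.25: 0.8690 − 0.7947 = 0.0742 (0.0743 from the rounded terms)

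The subtractions also give the properties of a cut-off of 8: type I error 0.039 and power 79.5%.

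**Step 4. The two-stage sampling.** Inverting the two-stage tail moves the exact 90% lower limit at 7/40 from 0.0851 to 0.0874, a shift of 0.23 percentage points. I also computed the coverage of the ordinary exact 90% interval with a binding stage 1 stop, using n = 16 after a stop and n = 40 otherwise. Over true rates from 0.005 to 0.60 its minimum is 0.890, near p = 0.27.

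**The case for a change.** The strongest case for a change is this. The interval sits in the primary-analysis section, without a label, and the plan does not say in words which output governs. The outcome concerned is the decision boundary itself. At a true rate of 10% it makes up 0.0499/0.0890 = 56% of all rejections, and at true rates between 15% and 20% it occurs about 13% to 14% of the time. No usual 90% method removes the disagreement, and an explanation written after a 7 of 40 result could look driven by the data. An 80% interval would put 10% in each tail, close to the test level, and would cost one line of text.

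The figures stand. The inference drawn from them does not:

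- The plan states one rejection criterion, the count of 7. An interval at a stricter level that still includes 10% is compatible with rejection at one-sided 0.089. It reports that the evidence would not have passed at 5%, which is true.
- The 79.5% power belongs to a cut-off of 8, which the plan does not contain. The trial's power remains 86.9%.
- The 56% is a share of a small total. The absolute probability under the null is 5.0%.
- The 80% interval buys agreement narrowly. The exact 80% lower limit clears 10% by 0.0001 (0.1001), and the Wald 80% limit fails (0.0980). The exact match to 0.089 is about an 82.2% two-stage interval (100 − 2 × 8.9). In return, the exact upper limit in the headline result falls from 30.4% to 27.7% only because less confidence is claimed.
- A two-stage interval assumes that the trial stops at 1 or fewer responses. Section 13.1 only convenes a study team at that point.

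**Conclusion.** No change to the plan follows. The 90% interval and the one-sided 0.089 test are not matched in level, and at exactly 7 of 40 the rule rejects 10% while the usual 90% intervals contain it. That has probability 7.4% at the design alternative of 25% and 5.0% at the null of 10%. The decision rule, its stated error rate and power, and the interval as an estimate are all sound as written.

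Reporting a conventional two-sided 90% interval beside a count-based decision is a fair trade-off. A clause saying that the count decides and the interval describes would only state what the section already implies. The unnamed interval method is a gap that an analyst fills sensibly with an exact method. Allowing for the two stages moves the lower limit at 7 of 40 from 8.5% to 8.7%, and the ordinary exact interval keeps at least about 89% coverage under the design.

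This rests on two assumptions. The first is that the conclusion is drawn from the 7-of-40 rule, the only criterion given. The second is that the interval is exact or another standard method other than Wald; with Wald the disagreement would extend to 8 of 40. If the trial continues after 1 or fewer responses in stage 1, the type I error could reach 0.0995, which leaves the argument unchanged.

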13.3 Monitoring

To minimize the risks of preoperative SBRT, safety will be monitored by A Bayesian stopping rule for the rate of acute toxicity grade ≥ 3 convincingly greater than 10%. Specifically, the Bayesian toxicity monitoring rule that suspends the accrual any time if the posterior probability of acute toxicity grade ≥ 3 risk being larger than 10% is 75% or higher. We assume a priori that this experimental regimen has an average risk around 5% and there is about 10% chance that the risk will be 10% or higher. This corresponds to a Beta (1,20) prior distribution. The following table gives the corresponding stopping rule for the 40 patients. For example, if 3 patients out of the first 5 treated patients experience acute toxicity grade ≥ 3 , we will suspend accrual temporarily and the principle investigators and study team will review the toxicity data and recommend either modification or termination of the trial.

# patients with toxicity	3	4	5	6	7
Out of total # patients treated	5	6-14	15-22	23-31	32-40

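### The type I error of 0.089 and power of 86.9% assume a mandatory stop at 1 or fewer responses in 16, but Section 13.1 leaves that stop to a study team; if the study proceeds to 40, type I error can reach 0.0995

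*Combined protocol and SAP*

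**What the plan says.** Section 13.1 names the design: "Simon's two-stage design (Simon, 1989) will be used". The hypothesis is set as "The null hypothesis that the true response rate is 0.1 will be tested against a one-sided alternative". On the first stage it says "In the first stage, 16 patients will be accrued", and at the lower boundary "If there are 1 or fewer responses in these 16 patients, a study team will be convened to determine if the study should proceed". For the other branch it says "Otherwise, 24 additional patients will be accrued for a total of 40". The final rule is "The null hypothesis will be rejected if 7 or more responses are observed in 40 patients", and the operating characteristics follow: "This design yields a type I error rate of 0.089 and power of 86.9% when the true response rate is 0.25".

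The section gives no criteria for the team's decision and no nominal limit for alpha. It does not say that the two operating characteristics presuppose a stop, and it does not say whether a study that proceeds past the boundary may still reject the null hypothesis. The only total sample size in the plan is 40. Section 13.3 uses the same total for toxicity monitoring: "The following table gives the corresponding stopping rule for the 40 patients".

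**The concern.** In a Simon design, the type I error and power are calculated on the footing that a trial at or below the first-stage boundary ends and cannot reject. Here that outcome triggers a discussion instead. A trial with 0 or 1 responses in 16 that is allowed to proceed can still reach 7 of 40, and the rejection sentence carries no condition on the first-stage count. Each such trial adds to the probability of rejection, under the null as well as under the alternative. The printed figures would then describe a stricter rule than the one written.

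At stake is the error rate that readers will attach to the primary conclusion, which the plan gives to three decimals. There is also a practical question that should be settled in advance: whether 7 of 40 counts as a positive result after a first-stage count of 0 or 1.

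**Working it through.** **Inputs, all from Section 13.1.** Null rate 0.10, one-sided; alternative rate 0.25; first stage 16 patients with boundary 1 or fewer; second stage 24 patients; total 40; reject at 7 or more.

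Let X1 ~ Bin(16, p) and X2 ~ Bin(24, p) be independent. All results are exact binomial.

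**1. Reproduce the plan's figures, with a mandatory stop.**

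P(reject) = sum over x = 2 to 16 of P(X1 = x) × P(X2 ≥ 7 − x)

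- p = 0.10: 0.08902 (plan: 0.089)
- p = 0.25: 0.86895 (plan: 86.9%)

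Both match, so the printed figures belong to the rule with a mandatory stop.

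**2. Opposite extreme: the team always continues to 40 with cut-off 7.** The first-stage boundary then has no effect, and P(reject) = P(Bin(40, p) ≥ 7).

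- p = 0.10: 0.09952, which is 0.01049 more before rounding
- p = 0.25: 0.90378, which is 0.03482 more before rounding

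**3. Source of the difference.** Each boundary count x contributes P(X1 = x) × P(X2 ≥ 7 − x).

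| First-stage count | p = 0.10 | p = 0.25 |
|---|---|---|
| 0 of 16 | 0.18530 × 0.00746 = 0.00138 | 0.01002 × 0.39259 = 0.00393 |
| 1 of 16 | 0.32943 × 0.02766 = 0.00911 | 0.05345 × 0.57784 = 0.03089 |
| Sum | 0.01049 | 0.03482 |

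**4. Range over the team's behaviour.** If the team continues with probability q0 after 0 responses and q1 after 1 response, the rejection probability is the value in step 1 plus q0 and q1 times the two contributions in step 3. These contributions are positive, so every such rule lies between steps 1 and 2.

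| Team's behaviour at the boundary | Type I error (p = 0.10) | Power (p = 0.25) |
|---|---|---|
| Always stops | 0.0890 | 86.9% |
| Continues in half of the cases | 0.0943 | 88.6% |
| Continues only after exactly 1 response | 0.0981 | 90.0% |
| Always continues | 0.0995 | 90.4% |

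**5. How often the team would meet.** P(X1 ≤ 1) is 0.5147 at p = 0.10 and 0.0635 at p = 0.25. This is the chance that the decision arises, not the chance of a false rejection. Among boundary trials under the null, only 0.0105 / 0.5147 = 2.0% would go on to reject even if all of them continued.

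**The case against.** The strongest reply is that nothing has been miscalculated. The section names Simon's design, and the figures are right for it. Read literally, the 24 further patients are assigned only to trials with 2 or more responses. For a trial at the boundary the text gives no sample size, no cut-off and no right to reject, so 0.0995 rests on a reading that the plan does not state. If an override barred rejection, 0.089 and 86.9% would both stand. The upper limit also requires the team to continue every time, even after 0 of 16. No stated alpha limit is breached, and power can only gain.

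Much of this stands. The arithmetic is correct for a mandatory stop, the effect is small, and 0.0995 is an upper limit under a stated reading. The 40 patients in Section 13.3 refer to the toxicity table, so they support that reading only indirectly.

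It does not remove the point. The plan expressly allows the study to proceed, and no total other than 40 is given for such a study. The rejection sentence has no first-stage condition, and nothing says that an override forfeits rejection. If the literal reading is the right one, the plan has no decision rule for a case that arises in about half of trials under the null. On either reading, a sentence is missing.

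**Conclusion.** The concern holds. Section 13.1 gives the operating characteristics of a mandatory stop for a boundary that it leaves to discretion. If a study that proceeds goes to 40 patients with cut-off 7, type I error is between 0.0890 and 0.0995 and power between 86.9% and 90.4%. The stated type I error is then the minimum of its range, and the understatement is at most 0.0105, or about 12% in relative terms (0.0995 / 0.0890 = 1.118). The stated power is also a minimum, which is the safe direction.

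This rests on three assumptions: the cut-off stays at 7 of 40 whenever the study proceeds, an override does not bar rejection, and the team decides without knowledge of second-stage responses. The design, sample size and cut-off are not in question; the stated figures are.

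**What to change.** In Section 13.1, choose one of the following.

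1. Make the stop at 1 or fewer of 16 mandatory and keep 0.089 and 86.9%. The cost is the team's discretion at the boundary.
2. Call the boundary non-binding, state that 40 patients and the cut-off of 7 apply whenever the study proceeds, and restate the figures: type I error at most 0.0995; power at least 86.9%, up to 90.4% if the study always continues. The cost is a slightly less favourable type I error.

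If the investigators want to keep both the discretion and the present figures, the text would have to say that the null hypothesis cannot be rejected once the boundary has been overridden. Merely adding that the figures assume a stop would label them correctly, but would leave open which rule applies after an override.

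Each choice takes one or two sentences and leaves the sample size and cut-off unchanged.

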13.2 Analysis of secondary objectives

Acute toxicities (up to 90 days after completion of surgery) will be collected using CTCAE v4.0 and will be tabulated by body system, type and grade. The number and percentage of patients who experience at least one grade 3 or higher AE will also be reported. The presence or absence of all CTCAE toxicities included in Appendix 15.2 will be assessed in addition to those listed here: breast pain, dermatitis, atrophy, fatigue, fibrosis, lymphedema, pruritis, seroma, surgical wound dehiscence, fat necrosis, surgical site infection, hyperpigmentation, skin ulceration. We will use continuous toxicity monitoring throughout the trial as described below. Stopping rules are described below in 13.3.

Local recurrence rates will be calculated using cumulative incidence function, where death without local recurrence is considered as competing event. The associated 95% confidence intervals at landmark timepoints including 6 months, 1 year, 2 years and 3 years will also be provided.

Physician assessment of cosmesis (see Section 9.3) will occur at baseline, 4-6 weeks after surgery, 6 months, 1, 2 and 3 years. The secondary endpoint of poor cosmetic outcome is a physician-assessment of unacceptable (fair or poor) cosmesis at any time point through 3 years and/or occurrence of grade 3 or higher toxicity through 3 years. The number and percentage of patients, with 2-sided x% CIs, will be reported. The timepoint of unacceptable cosmesis assessment and of the grade 3 or higher AEs will be summarized descriptively. Additionally, when all enrolled subjects have had 1 year of follow-up, a working group of investigators will be assembled to evaluate cosmesis on all patients.

Patient-reported satisfaction with cosmetic outcome will be assessed at baseline, 6 months, 1, 2 and 3 years. Satisfaction over time will be summarized descriptively and graphically.

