2.2 SECONDARY OBJECTIVES

2.2.1 To determine the rate of severe acute toxicity, defined as any CTCAE v4 grade 3 or higher toxicity noted from RT delivery up to 90 days after completion of surgery.

2.2.2 To determine the rate of poor cosmetic outcomes from both provider and patient perspectives up to 3 years after pre-operative SBRT to intact breast tumors using the RTOG (Radiation therapy oncology group) cosmesis scale and digital images.

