6.10 DURATION OF FOLLOW-UP

October 10, 2023

Principal Investigator: [name]

IRB IRB00128074

Follow-up for this study includes physical exam by member of oncology team every 6 months for the first 2 years, every 6-12 months through year 5, and annually through year 10. Bilateral mammogram will be obtained annually. Other laboratory or radiographic studies will be obtained as directed by patient symptoms or physical exam. Quality of life and cosmetic assessments by both physician and patient will be performed at 6 months, 1 year, and then annually through 3 years of follow-up. Loco regional recurrence will be monitored on protocol at each follow-up visit. Please see study calendar, section 8.0, for detail. Standard follow-up should continue per NCCN guidelines, off protocol, after 3 years.

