7. EXPECTED TOXICITIES

7.1 POSSIBLE TOXICITIES FROM RADIATION

7.1.1 Potential Short Term Reactions

Common:

- Skin redness and irritation in area treated
- Darkened skin and dryness in area treated
- Fatigue
- Temporary hair loss in the area treated
- Occasional aches and pains in the breast
- Temporary edema in treated breast

Uncommon:

- Post-operative bleeding at the time of surgery
- Increased risk of post-operative wound infection
- Seroma formation
- Skin blistering or ulceration

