- d. BCTOS to be completed by patient at baseline (prior to treatment), at first FU 4-6 weeks after surgery, six months and one year after surgery, and then annually for 2 additional years.
- e. RTOG cosmesis scoring to be completed by physician and patient at baseline (prior to treatment), at first FU 4-6 weeks after surgery, six months and one year after surgery and then annually for 2 additional years.

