9. CRITERIA FOR EVALUATION AND ENDPOINT DEFINITIONS

9.1 PATHOLOGIC RESPONSE – Standard pathologic assessment per our institutional guidelines will be followed. Additionally, we will include calculation of percent cellularity on the biopsy specimen, residual cancer burden (RCB) analysis and repeat evaluation of Ki67 and receptor status (ER, PR and Her2) if there is any residual invasive cancer at surgery. Residual cancer burden will be assessed by staff pathologists and is calculated using a published continuous index that combines pathologic measurements of the primary tumor (size and cellularity) and nodal metastases (number and size) (reference Symanns). This RCB index has been validated as a predictor of distant relapse.

9.2 ACUTE TOXICITY- Acute toxicity will be graded with the Common Terminology Criteria for Adverse Events (CTCAE) version 4. Grade ≥ 3 acute toxicity will be considered severe (Appendix 15.2).

9.3 COSMESIS- As noted in the introduction, early cosmetic results from other published pre-operative radiation series for early stage breast cancer have been favorable.¹¹ We expect similar favorable outcomes, and for the pre-operative single fraction cosmetic results to be equivalent to that of partial breast radiation results. We expect cosmesis to stabilize at 3 years following treatment and thus our endpoint will be to measure results at this timepoint. We will also assess cosmesis at specified time points per the study calendar to quantify changes in breast cosmesis over time.

Cosmetic results will be evaluated by both the patient and the physician. Patients will rate cosmesis using the Breast Cancer Treatment Outcome Scale (BCTOS), which will also be used to evaluate patient reported quality of life (Appendix 15.1). This self-report instrument has been used in a number of studies for this purpose and has both reliability and validity (reference Stanton AL, Krishnan L, Collins CA. Form or function? Part 1. Subjective cosmetic and functional correlates of quality of life in women treated with breast-conserving surgical procedures and radiotherapy. *Cancer* 91:2273-2281, 2001)

October 10, 2023

Principal Investigator: [name]

IRB IRB00128074

Patients will first complete this after informed consent, and then at multiple intervening assessment points up to 3-years of follow-up (see Study Calendar). At the same time points, patients will also score cosmesis using the RTOG 4-point scale.

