Appendix 15.3.1 RTOG cosmesis scale- PHYSICIAN FORM

1	EXCELLENT: when compared to the untreated breast or the original appearance of the breast, there is minimal or no difference in the size or shape of the treated breast. The way the breast feels (its texture) is the same or slightly different. There may be thickening, scar tissue or fluid accumulation within the breast, but not enough to change the appearance.
2	GOOD: there is a slight difference in the size or shape of the treated breast as compared to the opposite breast or the original appearance of the treated breast. There may be some mild reddening or darkening of the breast. The thickening or scar tissue within the breast causes only a mild change in the shape or size.
3	FAIR: obvious differences in the size and shape of the treated breast. This change involves a quarter or less of the breast. There can be moderate thickening or scar tissue of the skin and the breast, and there may be obvious color changes.
4	POOR: marked change in the appearance of the treated breast involving more than a quarter of the breast tissue. The skin changes may be obvious and detract from the appearance of the breast. Severe scarring and thickening of the breast, which clearly alters the appearance of the breast, may be found.

(Circle the number next to the word that best describes the cosmetic results.)

	None	Yes, present but does not affect cosmesis	Yes, present and affects cosmesis
Skin telangiectasia	0	1	2
Skin atrophy	0	1	2
Pigment change	0	1	2
Erythema	0	1	2
Fat necrosis	0	1	2
Fibrosis	0	1	2
Retraction or contour defect	0	1	2
Breast shrinkage	0	1	2
Other significant tx effects Specify: _____	0	1	2

October 10, 2023

Principal Investigator: [name]

IRB IRB00128074

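### Section 13.2 counts any single post-treatment fair or poor physician rating, even at 4-6 weeks after surgery, as a poor cosmetic outcome through 3 years, whereas 9.3 sets the endpoint at 3 years

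*Combined protocol and SAP*

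**What the plan says.** Section 13.2 defines the secondary endpoint of poor cosmetic outcome as a composite. One part is a "physician-assessment of unacceptable (fair or poor) cosmesis at any time point through 3 years"; the other is any grade 3 or higher toxicity over the same period. Either part is enough. The number and percentage of patients are to be reported with a two-sided CI whose level is still a placeholder.

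The ratings that feed the first part are listed just before: "Physician assessment of cosmesis (see Section 9.3) will occur at baseline, 4-6 weeks after surgery, 6 months, 1, 2 and 3 years". The calendar in Section 8 marks the physician RTOG rating in the 4-6 week column, and its footnote e confirms it. No section asks for a second rating, leaves out the early visit, or lets a later good or excellent rating cancel the event.

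Section 9.3 describes a different endpoint: "We expect cosmesis to stabilize at 3 years following treatment and thus our endpoint will be to measure results at this timepoint". Assessments at the other visits are there to quantify change over time. Objective 2.2.2 is worded more broadly: "To determine the rate of poor cosmetic outcomes from both provider and patient perspectives up to 3 years". Section 6.10 summarises the schedule without the early visit ("Quality of life and cosmetic assessments by both physician and patient will be performed at 6 months, 1 year, and then annually through 3 years"), but refers the reader to the calendar for detail.

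Section 7.1.1 lists skin redness, skin darkening and "Temporary edema in treated breast" as common short-term reactions, and seroma as uncommon.

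**The concern.** The 4-6 week visit comes soon after an excision and within the period that objective 2.2.1 treats as acute. A marked but temporary change at that visit makes the patient a permanent event. She then counts the same as a patient rated fair at 1, 2 and 3 years. The reported percentage and its CI would therefore mix early healing, isolated ratings and lasting change, although 9.3 says the question is how the breast looks once cosmesis has settled.

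Section 9.3 also expects results equivalent to those of partial breast radiation, and the background quotes patient satisfaction at 3 years from the preoperative series with 10 fractions. A worst-ever rate is hard to set beside a 3-year figure. With 40 patients, each transient event adds 1/40 = 2.5 percentage points.

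**Working it through.** **Plan's own figure.** The cosmesis endpoint has no target rate, hypothesis or power, so there is nothing to reproduce. The only design figures (type I error 0.089, power 86.9% in 13.1) belong to the pathologic endpoint. They reproduce by exact binomial calculation with a binding first-stage stop (0.0890 and 0.8690) and have no bearing here.

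**Timing.** 4-6 weeks is day 28-42 after surgery, inside the 90-day window of 2.2.1. Time since SBRT is less clear. Section 6.5 puts surgery 7-14 days after radiation, which places the visit 5-8 weeks after SBRT. Section 6.9 puts surgery 4-6 weeks after radiation, which gives 8-12 weeks. Those two sections must be reconciled, but the point rests on time since surgery, which does not change.

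**What each definition counts** (cosmesis component only; visits are 4-6 weeks and Months 6, 12, 24, 36):

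| Rating pattern | 13.2, any visit | 9.3, at 3 years | Month 6 or later | Two consecutive from Month 6 |
|---|---|---|---|---|
| A: fair at 4-6 weeks, then excellent | event | no | no | no |
| B: good except one fair at Month 12 | event | no | event | no |
| C: fair at Months 12, 24 and 36 | event | event | event | event |
| D: good until a first fair at Month 36 | event | event | event | no (no later visit) |

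Section 13.2 does not separate the four. Section 9.3 counts only C and D.

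**What could be rated fair at 4-6 weeks.** On the physician form, mild reddening or darkening falls under GOOD, and fluid that leaves the appearance unchanged falls under EXCELLENT. FAIR is led by obvious differences in size and shape, with the addition that "there may be obvious color changes". So obvious edema, or a seroma that alters size and shape, could qualify; mild reactions should not.

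**Size, by assumption.** Let L be the lasting fair/poor rate and t the chance of a transient fair/poor rating at 4-6 weeks only, taken as independent. The documents give neither.

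Reported rate = 1 − (1 − L)(1 − t). With L = 5%, the 3-year endpoint expects 40 × 0.05 = 2.0 events.

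| t | Reported rate | Expected events of 40 | Nearest count, exact 95% CI |
|---|---|---|---|
| 0 | 5% | 2.0 | 2/40: 0.6-16.9% |
| 5% | 1 − 0.95 × 0.95 = 9.75% | 3.9 | 4/40: 2.8-23.7% |
| 10% | 1 − 0.95 × 0.90 = 14.5% | 5.8 | 6/40: 5.7-29.8% |
| 20% | 1 − 0.95 × 0.80 = 24% | 9.6 | 10/40: 12.7-41.2% |

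The 95% level is also an assumption, since 13.2 leaves it open. If t = 0, the early visit makes no difference.

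**Isolated ratings, by assumption.** Let q be the chance of a stray fair/poor rating at each visit, independent across visits, with no true poor cosmesis.

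- Five post-treatment visits: 1 − (1 − q)^5 = 4.9%, 9.6% and 22.6% for q = 1%, 2% and 5%.
- Four visits from Month 6: 1 − (1 − q)^4 = 3.9%, 7.8% and 18.5%.
- Month 36 alone: q, that is 1%, 2% and 5%.
- Two consecutive of the four: 1 − [(1 − q)^4 + 4q(1 − q)^3 + 3q²(1 − q)²] = 0.03%, 0.12% and 0.72%.

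Dropping the early visit deals with acute reactions but does little about stray ratings. The 3-year rate and the consecutive-visit row address those.

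**The case against.** The strongest reply is that an any-time rate is a legitimate cumulative measure. It matches the up-to-3-years wording of objective 2.2.2, and the toxicity half of the composite is counted in the same way. The endpoint is secondary and no trial decision depends on it. Section 13.2 will also summarise when unacceptable ratings occurred, 9.3 plans to describe change over time, a working group will evaluate cosmesis once all patients have 1 year of follow-up, and images are taken at 1 and 3 years. Early-only events would therefore be visible.

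Most of this stands. The any-time rule is not an error in itself, and a careful reader could trace the early events. It does not remove the conflict with 9.3, and the descriptive summaries do not change the reported percentage or its CI.

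The case also should not lean on 6.10. A reader might infer that 6.10 settles a 6-month start. It does not: it defers to the calendar, and the calendar agrees with 13.2 on the early visit. More telling is that 13.2's own analysis of patient-reported satisfaction uses baseline, 6 months and 1, 2 and 3 years, without the early visit, although patient ratings are collected then.

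**Conclusion.** The point holds as a conflict of definition between 9.3 and 13.2. As written, 13.2 lets one unconfirmed rating in the acute window enter the headline percentage for good. The size is unknown. The range of 9.75% to 24% against a lasting 5% rests on assumed, independent rates and leaves out the toxicity component, so it is not a forecast of the endpoint.

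Three stronger readings are not supported:

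- A reader might infer that the reactions expected in 7.1.1 will routinely be reported as poor cosmesis. The RTOG form places the mild ones under GOOD or EXCELLENT.
- A reader might infer, because the cited phase I series rated every patient excellent or good, that most counted events will be transient or spurious. A 32-patient series with no fair or poor ratings does not show that transient ones occur.
- A reader might infer that the reported rate can only be too high. Missed visits and withdrawals can lower an ever-event percentage, and no rule for missing ratings is given.

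The change is worth making because it is cheap and lets the result answer the question that 9.3 poses.

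**What to change.** Reconcile 9.3 with 13.2, and bring the summary in 6.10 into line with the calendar. In 13.2:

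1. Report fair or poor physician cosmesis at 3 years, with its CI, as the lasting-cosmesis result that 9.3 names. State the number of patients rated at that visit.
2. Limit the cumulative cosmesis component to ratings at Month 6 or later.
3. Tabulate the 4-6 week rating separately, as early post-operative appearance.
4. Add a supportive row for patients rated fair or poor at two consecutive scheduled visits from Month 6. Note that a first such rating at Month 36 cannot be confirmed on protocol and still counts in the 3-year rate.
5. Report the grade 3 or higher toxicity component separately, so that acute toxicity is not read as lasting poor cosmesis.

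The cost is a few sentences and table rows, with no new visits or data. The downside is that early transient events leave the headline rate, though they remain tabulated. The wording should be settled before the cosmesis ratings are analysed, so that the definition is not chosen after the results are seen.
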